10 CONCOMITANT MEDICATIONS

Patients should receive full supportive care including transfusions of blood and blood products, antibiotics, anti-emetics, etc., where applicable. It is strictly mandated that patients not be given other myelosuppressive anti-neoplastic agents until recovery from hematologic nadir.

Patients receiving concurrent oral anticoagulant therapy should have this medication discontinued when the platelet counts fall below 30,000 cells/mm³. Oral anticoagulant therapy may be resumed upon signs of platelet recovery, at the discretion of the investigator.

11 REMOVAL OF PATIENTS FROM THIS STUDY

11.A Criteria for Discontinuation of a Patient's Study Participation

The date of discontinuation and reason(s) for patient discontinuation from the study will be recorded in the CRF. All evaluations which are required at the final study visit must by conducted for each patient who discontinues treatment, regardless of the reason (see Section 5.F.1).

- Disease Progression: Patients will be taken off study if they have progressive disease (PD) or clinically significant deterioration at any time during the study.
- Personal Reasons: Patients may choose to withdraw from the study at any time.
- Clinical Judgment of the Investigator: A patient may be withdrawn from the study, if in the opinion of the investigator, it is not in the patient's best interest to continue.
- Requiring other anti-neoplastic therapies

12 STATISTICAL CONSIDERATIONS

12.A Study Design

This is a two- institution phase II trial to determine the efficacy and safety of the ESHAP-Zevalin combination therapy for the management of relapsed (CD 20+) follicular lymphoma. Patients must have received at least one, but no more than 2 prior treatments for follicular lymphoma.

The primary objective of this phase II clinical trial is to evaluate the 1-year progression-free survival (PFS) of patients with relapsed follicular NHL treated with ESHAP chemotherapy for cytoreduction (2 cycles) followed by Y-90 ibritumomab tiuxetan (Zevalin) radioimmunotherapy, compared to what would be expected historically for patients treated with Zevalin without prior cytoreduction. For this patient population, a 1-year PFS of 67.3% will be considered highly encouraging, compared to an historical rate around 50%. These values correspond to approximate median times to progression of 21 months and 12 months, respectively, assuming exponential survival.

12.B. Sample Size

The planned sample size of 52 evaluable patients is based on testing the null hypothesis that the true 1-year PFS is \leq 50%, versus an alternative hypothesis that the true rate is \geq 67.3% with this therapeutic approach. Based on the number of patients seen at the Arizona Cancer Center with relapsed follicular lymphoma requiring treatment, the anticipated accrual rate is 2 patients per month. It is estimated that accrual to the study would be completed within 26 months. All patients who receive at least one dose of chemotherapy will be considered evaluable and included in the analysis. In the unlikely event that an enrolled patient does not receive treatment, an additional patient will be registered.

12.C Method of Analysis

The following are the design characteristics based on a chi-square test for one binomial population at the one-sided 0.10 significance level. If the true PFS is $\leq 50\%$, then there is a maximum probability of 0.10 of concluding that this treatment approach is sufficiently promising that it should be accepted for further study (false positive rate). Alternatively, if the true PFS is $\geq 67.3\%$, then the maximum probability of

rejecting this treatment approach for further study in this setting is 0.10 (false negative rate), equivalent to a power of 90%.

At the end of the trial, the observed PFS and response rates will be reported, along with appropriate confidence limits. Kaplan-Meier methods will be used to estimate the survival curve of time-to-progression. Promising results at the conclusion of this trial will justify further study in a larger trial.

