In a multi-center Phase I/II trial dose-finding study (106-03), Witzig et al treated 51 patients with relapsed or refractory non-Hodgkin's lymphoma with Ibritumomab Tiuxetan (Y2B8, Zevalen®).[78] Eligibility criteria included an ANC > 1,500/mm3, platelets > 100,000/mm3 and bone marrow involvement < 25%. Median age was 60 years. Patients had a median of two prior regimens (range, 1-7). In the phase I portion of the trial, patients received either 100 or 250 mg/m2 of unlabeled rituximab (to clear peripheral B-cells and improve biodistribution) followed by Indium-111ibritumomab tiuxetan (5 mCi on Day 1 for imaging and Y-90-ibitumomab tiuxetan 0.2, 0.3, or 0.4 mCi/kg on Day 8. The optimal dose of unlabeled rituximab was determined to be 250 mg/m2 and 0.4 mCi/kg was the maximally tolerated dose of Yttrium-90. In an intent-to- treat analysis the overall response rate was 67%, including 26% CRs and 41% PRs. Thirty-four patients with low grade lymphoma achieved an 82% overall response rate (26% CRs, 56% PRs), 43% of 14 aggressive lymphomas responded, and none of the three patients with mantle cell disease responded. Estimated time to progression for intent to treat was 12.9 months and estimated median duration of response was 11.7 months. Hematologic toxicity was dose-limiting. Thrombocytopenia was the most common hematologic event. Hematologic toxicity was transient and reversible. Only one patient developed an immune response.

Witzig et al $^{[79,80]}$ (106-04) conducted a randomized phase III trial in 143 patients with relapsed or refractory low-grade, follicular, or CD 20+ transformed NHL. Patients received either ibritumomab tiuxetan, 0.4 mCi/kg (maximum of 32 mCi) or rituximab, 375 mg/m2 weekly for 4 weeks. Eligibility required an ANC \geq 1,500/mm3, a platelet count \geq 100,000/mm3, and bone marrow involvement < 25%. As assessed by International Workshop Response Criteria, $^{[81]}$ patients who received ibritumomab tiuxetan achieved an overall response rate (ORR) of 80% (73 patients) compared with 56% (70 patients) for patients on the rituximab arm (p = 0.002). Complete response (CR) rates were 30% for the ibritumomab tiuxetan group and 16% for the rituximab group (p = 0.04), with an additional 4% of

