patients in each arm achieving an unconfirmed CR. The estimated (Kaplan-Meier) median duration of response was 14.2 months versus 12.1 months, respectively (p = 0.6) and time to progression (TTP) was 11.2 versus 10.1 months, respectively (p = 0.173). For the 113 patients with follicular histology (113 of the 143 patients), the overall response rate was 86% in the 90-Y- ibritumomab tiuxetan group versus 55% in the rituximab group (P < 0.001), and the estimated median TTP was 12.6 months for the 90-Y-ibritumomab tiuxetan group and 10.2 months for the rituximab group (P = 0.062). The estimated median DR for patients with follicular lymphoma patients treated with 90-Y ibritumomab tiuxetan was 18.5 months versus 12.1 months for the rituximab control group (P = 0.371. Durable responses of \geq 6 months were 64% versus 47% (P = 0.030), respectively. Although the differences in duration of response and TTP were not significant between arms, ORR and CR were significantly higher in the ibritumomab tiuxetan group. Time to progression was longer in CR/CRu patients treated with 90-Y-ibritumomab. Within the group of patients with follicular lymphoma 74% had DR \geq 6 months, 59% \geq 9 months, and 47% \geq 12 months on the 90-Y-ibritumomab tiuxetan arm. Reversible hematologic toxicity was seen in patients treated with ibritumomab tiuxetan.

In an open-label trial, [82, 82a] 54 patients with follicular lymphoma were accrued to learn whether patients who had failed to achieve a partial remission or CR (complete response) to rituximab or had a response that lasted less than 6 months would respond to radioimmunotherapy with Y-90-ibritumomab tiuxetan. The median age was 54 years and patients had received a median of four prior regimens. Forty-four percent of patients had bulky disease (defined as ≥ 7 cm) and 32% had bone marrow involvement. Using the International Workshop Response Criteria, the overall response rate was 74% with Y-90-ibritumomab tiuxetan and the complete response rate was 15%. The duration of response was 7.7 months for ibritumomab tiuxetan compared to 4 months for prior rituximab in these patients (p < 0.001). Median time to progression had not been reached at the time of the report.

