Second, although ESHAP is very active in low-grade NHL, it is not often utilized by community oncologists as a salvage regimen. Therefore, most pretreated patients have not seen these agents and therefore their lymphomas should be responsive to ESHAP. After treatment with two cycles of preparative ESHAP most patients should have minimal residual disease and therefore have higher response to Zevalin. It is our hypothesis that tumor mass reduction with standard chemotherapy in relapsed follicular lymphoma will result in a significant prolongation of time to progression following Zevalin therapy, changing the natural history of relapsed disease.

The TTP and OS results of this study will be compared with reported outcomes in published trials of Zevalin alone to assess whether there is sufficient improvement to merit further study of this approach in this setting. We have designed the trial to detect an increase in 1-year PFS from a historical value of 50% to 67.3%, which corresponds to an increase in median TTP from 12 months to 21 months.

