4 STUDY POPULATION

4.A Inclusion Criteria

- 4.A.1 All patients must have a history of relapsed follicular non-Hodgkin's lymphoma. Patients must be in first, second, third, or fourth relapse.
- 4.A.2 Lymphomas must express the CD20 antigen as demonstrated by either flow cytometry or immunoperoxidase staining of paraffin sections using anti-CD20 antibodies.

- 4.A.3 Patients must have bulky Stage II, Stage III, or Stage IV extent of disease by the Ann Arbor classification (see Appendix F). Bulky disease is defined as any tumor measuring 10.0 cm or greater or occupying ≥ one-third of the chest diameter.
- 4.A.4 All patients must have bidimensionally measurable disease (as defined in Appendix D) documented within 28 days prior to C1, Day 1.
- 4.A.5 Pathology Review: Adequate sections from the diagnostic specimen or core needle biopsies which are large enough to show architecture (bone marrow biopsies and fine-needle aspirates are insufficient) is desirable. At a minimum, a report documenting the diagnosis is required.
- 4.A.6 Patients must have a unilateral or bilateral bone marrow aspirate and biopsy performed within 28 days prior to Cycle 1, Day 1.
- 4.A.7 Patients must have a CT or PET scan of chest, abdomen, and pelvis within 28 days prior to Cycle 1, Day 1.
- 4.A.8 Patients must have an LDH and β-2 microglobulin within 28 days prior to Cycle 1, Day 1.
- 4.A.9 Patients must have received prior chemotherapy for lymphoma.

 (Patients must have had at least 1, but no more than 4 prior chemotherapy regimens for lymphoma. This includes investigational agents and/or other antibody therapy. All prior therapy must have been completed at least 3 weeks prior to registration. Patient who previously received rituximab must have completed this therapy 6 weeks prior to registration. If rituximab is given as a single agent after relapse, it is considered a separate regimen and will be counted as such. If the rituximab is given in combination for either the first or second relapse or as consolidation after a chemotherapy regimen without an intervening relapse, it will considered part of the combination regimen and counted as one prior therapy. Patients must have recovered from any prior-therapy-related toxicities prior to Cycle 1, Day 1.)
- 4.A.10 All patients must have a Zubrod performance status of 0, 1, or 2 (see Appendix B).
- 4.A.11 Patients must be 18 years old or older.

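### The Appendix A calendar grid omits the month-12 and month-24 disease assessments and scans that 5.E.1 calls for, which can inflate median TTP; separately, 12.A and 4.A state different limits on prior treatment

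*Combined protocol and SAP*

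**What the plan says.** **Assessment schedule.** Section 5.E.1 requires a disease assessment at 6-month intervals for 24 months after Zevalin and recommends CT restaging at the same interval, that is, at months 6, 12, 18 and 24. Section 3.A also describes 6-monthly follow-up for 2 years, and a footnote to page 2 of the Appendix A calendar says that examinations and tests recur every 6 months for 2 years.

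The grid on that page differs. Its Disease Assessment row and its CT/PET rows for chest, abdomen and pelvis are marked at 3, 6 and 18 months, at long-term follow-up and off study. They are blank at 12 and 24 months. The other six rows carry a mark in all seven columns, so the blanks do not look like cells lost in text conversion.

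Sections 2.A.1 and 2.A.2 make both 1-year PFS and median TTP primary objectives. Appendix D (Measures of Duration) runs TTP from first study treatment to the first date on which progression is documented.

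**Population.** Section 12.A states "Patients must have received at least one, but no more than 2 prior treatments for follicular lymphoma" and, two sentences later, "For this patient population, a 1-year PFS of 67.3% will be considered highly encouraging, compared to an historical rate around 50" percent. Section 4.A.1 says "Patients must be in first, second, third, or fourth relapse" and 4.A.9 says "Patients must have had at least 1, but no more than 4 prior chemotherapy regimens for lymphoma". Section 1.E says that the TTP and OS results "will be compared with reported outcomes in published trials of Zevalin alone".

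**The concern.** The calendar is the page a site is likely to work from. A site that follows the grid performs no scheduled imaging between months 6 and 18 after Zevalin; a site that follows 5.E.1 images at month 12 as well. TTP is dated at documentation, so a longer gap between scans moves the recorded date later without any change in the disease. The design values are medians of 12 and 21 months, and the gap covers most of the interval between them. The result is to be set against published Zevalin-alone outcomes, so a delay produced by the schedule could be read as a treatment effect.

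The eligibility conflict is smaller. A patient with three or four prior regimens is eligible under 4.A but outside the population described in 12.A, so the population for the 50% versus 67.3% test is described in two ways.

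**Working it through.** **1. The plan's own figures.** Inputs from 12.A-12.C: p0 = 0.50, p1 = 0.673, one-sided alpha 0.10, power 0.90.

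n = [(1.2816·√(0.5·0.5) + 1.2816·√(0.673·0.327)) / 0.173]² = 51.54, rounded up to 52. This reproduces the stated N; approximate power at 52 is 90.2%. The exponential median for 67.3% is 12·ln(0.5)/ln(0.673) = 21.0 months, as stated. Neither the scan schedule nor the prior-treatment limit enters these formulas.

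**2. Scan times from Cycle 1 Day 1.** Section 7.B places the Zevalin regimen 4-6 weeks after ESHAP is completed, with the 90Y dose on day 7, 8 or 9. Assuming no delays and 28-day cycles, the lead L to 90Y is 65-81 days if completion means Cycle 2 Day 4, or 89-105 days if it means the end of cycle 2. So L is about 2.1-3.4 months.

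| Scan after Zevalin | Months from C1D1 | 5.E.1 | Grid |
|---|---|---|---|
| Month 6 | 8.1-9.4 | yes | yes |
| Month 12 | 14.1-15.4 | yes | blank |
| Month 18 | 20.1-21.4 | yes | yes |

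**3. Survival at those times**, with the exponential form that 12.A assumes and a true median of 12 months, S(t) = 0.5^(t/12): S(8.1) = 0.626, S(9.4) = 0.581; S(14.1) = 0.443, S(15.4) = 0.411; S(20.1) = 0.313, S(21.4) = 0.291.

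**4. Documented 1-year PFS.** Let c be the share of progressions found on time between scans, the rest being found at the next scan. The documented curve is c·S(t) + (1−c)·S(last scan before t). At t = 12 the last scan is month 6 after Zevalin in both schedules. With c = 0 the documented value for a true 50% is 0.626 (L = 2.1) or 0.581 (L = 3.4); with c = 0.5 it is 0.563 or 0.541; with c = 1 it is 0.500. The schedules give identical values. In patients, (0.626 − 0.500)·52 = 6.6 and (0.581 − 0.500)·52 = 4.2 could be read as progression-free at 1 year under either schedule if detection is by scan only.

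**5. Documented median TTP for a true 12 months.** Set the documented curve to 0.5.

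- c = 0: the curve first falls below 0.5 at the next scan, which is 14.1-15.4 months under 5.E.1 and 20.1-21.4 under the grid. The result is the same at c = 0.25.
- c = 0.5, L = 2.1: 0.5·S(t) + 0.5·0.626 = 0.5 gives S(t) = 0.374 and t = 17.0. Under 5.E.1 the 14.1-month scan comes first, so the medians are 14.1 and 17.0.
- c = 0.5, L = 3.4: S(t) = 0.419 and t = 15.1, before the 15.4-month scan, so both are 15.1.
- c = 0.75: 13.5 (L = 2.1) and 13.0 (L = 3.4) in both schedules.

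The schedules agree once c reaches (0.626 − 0.5)/(0.626 − 0.443) = 0.69 at L = 2.1, or (0.581 − 0.5)/(0.581 − 0.411) = 0.48 at L = 3.4. The full delay to month 18 needs c below 0.126/0.313 = 0.40 or 0.081/0.290 = 0.28 respectively.

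**6. Does the population conflict move the benchmark?** Under exponential survival, 1-year PFS = 0.5^(12/m) for a median m. For study 106-03, "Estimated time to progression for intent to treat was 12.9 months" implies 0.525. For the follicular subset of 106-04, "the estimated median TTP was 12.6 months for the 90-Y-ibritumomab tiuxetan group" implies 0.517. The 11.2 months for the whole Zevalin arm of 106-04 gives 0.476, and the 10.8 months for follicular patients in the mild-thrombocytopenia study gives 0.463. The range of 46%-52% surrounds the 50% null. Study 106-03 included patients with 1-7 prior regimens, so that series at least was not restricted to two.

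**The case against.** The strongest reply is that the intended schedule is clear: 3.A, 5.E.1 and the calendar footnote all say 6-monthly, and only the grid differs. No document shows that any site acted on the blanks. That stands, and it makes this a correction of the calendar rather than a dispute over design.

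The second reply is that the large TTP shift needs few progressions to be found between scans. History, physical examination and LDH remain marked at months 12 and 24. Appendix D counts an enlarging liver or spleen and new sites as progression, and section 11.A removes patients for clinical deterioration at any time. This also stands: some detection between scans is plausible, and the documents give no figure for it. The 20.1-21.4 month result is therefore the upper end of a range that reaches zero.

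A reader might infer that the gap, because it spans 1 year, biases the 1-year PFS test. The documents do not support that. The grid does put more patients between the scans either side of 1 year (15-16 of 52, against 9-10 under 5.E.1, at the null). The extra patients, however, progress after the 14.1-15.4 month scan time and are progression-free at 1 year under either schedule.

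On 12.A, the amendment log records that 4.A.1 and 4.A.9 were widened deliberately, and registration checks the section 4 criteria. The sentence is probably one that was not updated. That explains the conflict but does not remove it.

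**Conclusion.** Both contradictions are present in the current text. The calendar grid is the one with a possible numerical consequence. Relative to 5.E.1, it leaves documented 1-year PFS unchanged but can lengthen documented median TTP. For a true 12-month median the excess is about 6 months if progression is found only at scans. If half of progressions are found on time it is between 0 and 2.9 months (15.1 vs 15.1, or 17.0 vs 14.1, depending on the lead time). At three-quarters it is nil. These figures assume exponential progression, no treatment delays, scans exactly on schedule, and sites following the grid literally.

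The prior-treatment conflict changes no number. A reader might infer that the 50% null is wrong for patients with three or four regimens, or that power is lost. The documents give no outcome by number of prior regimens, and the cited Zevalin-alone medians fit 50%. They report prior-regimen counts for 106-03 and for the rituximab-refractory trial (median four, TTP not reached), but not for the series with medians of 12.6 and 10.8 months. The benchmark is therefore neither refuted nor fully documented for the 4.A population. N = 52, the test and its power stand.

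**What to change.** In Appendix A, page 2, reconcile the Disease Assessment row and the three CT/PET rows with 5.E.1 and the calendar's footnote, so that one 6-monthly assessment schedule is in force to month 24. This is a text edit. If sites have followed the grid, the month-12 and month-24 scans are extra against current practice, although 5.E.1 already lists them. The month-12 scan shortens the gap around 1 year but does not place a scan at 12 months from entry.

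Secondarily, reconcile the prior-treatment sentence in 12.A with 4.A.1 and 4.A.9, so that the population for the 50% versus 67.3% comparison is described in one way. Which limit applies is for the sponsor to state. N, the primary test, the power and the time origin need no change.

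### Section 12.C states a maximum false-positive rate of 0.10, but the chi-square rule behind n = 52 rejects from 31/52, where the exact rate is 10.6%; the cut-off itself is not written down (minor)

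*Combined protocol and SAP*

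**What the plan says.** Section 12.A sets a 1-year PFS of 67.3% as the encouraging value, "compared to an historical rate around 50" per cent. Section 12.B gives "The planned sample size of 52 evaluable patients" for testing a true rate of at most 50% against one of at least 67.3%.

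Section 12.C describes the design as "based on a chi-square test for one binomial population at the one-sided 0.10 significance level". It then states two error rates as limits:

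- False positive, true PFS at or below 50%: "then there is a maximum probability of 0.10 of concluding that this treatment approach is sufficiently promising".
- False negative, true PFS at or above 67.3%: the maximum probability of "rejecting this treatment approach for further study in this setting is 0.10 (false negative rate), equivalent to a power of 90" per cent.

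On the decision itself, 12.C closes with "Promising results at the conclusion of this trial will justify further study in a larger trial". No count or proportion is given for what is promising, and 12.C does not mention a continuity correction.

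**The concern.** A count out of 52 moves in whole patients, so a test calibrated by the normal approximation rarely has exactly its nominal level. Giving the nominal 0.10 as a maximum probability is a stronger claim than calling the test a 0.10-level test, and it can be checked.

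The two error rates are the only numerical decision properties in Section 12. If one of them is a limit the rule does not keep, the plan should say what the rule does deliver. The missing cut-off adds to this. At the boundary count, the answer depends on a detail of the test that 12.C leaves open, and it is better settled before the results are seen.

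**Working it through.** **Inputs.** n = 52 (12.B); p0 = 0.50 and p1 = 0.673 (12.A, 12.B); one-sided alpha 0.10, power 0.90, one-sample chi-square test (12.C). The 0.90 normal quantile is 1.2816.

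**1. Reproduce the plan's sample size.** With the normal-approximation formula and no continuity correction,

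n = [(1.2816 × √(0.5 × 0.5) + 1.2816 × √(0.673 × 0.327)) / (0.673 − 0.50)]²

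= [1.2816 × (0.5 + 0.4691) / 0.173]² = 7.179² = 51.54, rounded up to 52.

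Approximate power at 52 is Φ[(0.173 × √52 − 1.2816 × 0.5) / 0.4691] = Φ(1.293) = 0.902. The plan's figure is reproduced. With a continuity correction the formula gives 57.2, hence 58, so the design was evidently built on the uncorrected test.

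**2. Find the cut-off.** Under p0 the count has mean 52 × 0.5 = 26 and variance 52 × 0.25 = 13. The test rejects above 26 + 1.2816 × √13 = 30.62, that is, from 31 of 52 (59.6%).

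- 30/52: z = (30 − 26)/√13 = 1.109, p = 0.134, not rejected.
- 31/52: z = (31 − 26)/√13 = 1.387, p = 0.083, rejected.
- 31/52 with continuity correction: z = (30.5 − 26)/√13 = 1.248, p = 0.106, not rejected.

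**3. Exact error rates** (binomial tail probabilities):

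| Rule | False-positive rate, p = 0.50 | Power, p = 0.673 |
|---|---|---|
| ≥ 30 of 52 | 0.166 | 0.946 |
| ≥ 31 of 52 | 0.1058 | 0.9064 |
| ≥ 32 of 52 | 0.0632 | 0.8492 |

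The rule that the named test implies has a false-positive rate 0.1058 − 0.10 = 0.0058 above the stated maximum. Its false-negative rate is 1 − 0.9064 = 0.094, inside the stated limit. Raising the cut-off to 32 keeps the first limit and breaks the second. No cut-off at n = 52 keeps both; the smallest n that does is 55 with at least 33 successes (0.0885 and 0.9012).

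**4. How sensitive is the excess?** For ≥ 31 of 52 the false-positive rate is 0.062 at a true rate of 48%, 0.082 at 49%, 0.106 at 50% and 0.135 at 51%. It equals 0.10 at 49.78%.

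**5. Unknown 1-year status.** The figures above assume the status is known for all 52. Section 12.B says "All patients who receive at least one dose of chemotherapy will be considered evaluable and included in the analysis", while Section 11.A says "Patients may choose to withdraw from the study at any time". Section 12.C does not say how a patient with unknown status enters the count. As an illustration on assumed numbers, keep the cut-off at 31 and count unknowns as not progression-free:

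| Unknown (assumed) | Distribution of the count | False-positive rate | Power |
|---|---|---|---|
| 0 | Bin(52) | 0.106 | 0.906 |
| 1 | Bin(51) | 0.080 | 0.872 |
| 2 | Bin(50) | 0.059 | 0.829 |

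**The case against.** The best defence is that 12.C introduces both rates as characteristics of a large-sample test at the 0.10 level. On that reading, maximum means the worst case over all true rates at or below 50%, at the nominal level, and the statement is consistent with the n of 52. It can be added that the historical rate is only approximate. One percentage point either way in that benchmark moves the false-positive rate between 8.2% and 13.5%, far more than the 0.6 points at issue. The cut-off can also be derived from the test, level, null and n already in Section 12, and n = 52 points to the uncorrected form. Finally, Section 1.E says TTP and OS will be compared with published Zevalin trials to judge whether further study is merited, so the binomial test is not the only statement about going forward.

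Most of this bears on weight, and there it stands: the discrepancy is negligible beside the uncertainty in the benchmark. It does not rescue the wording. An explicit maximum probability is a claim about the rule's actual behaviour, and at 50% the rule exceeds it. A reader can recover 31/52 only by working back from the sample size to infer that no continuity correction applies. Section 1.E supplies no competing cut-off or error rate. A fair practical caution is that a bare count covers only n = 52, so the level-based test should stay in the text beside it.

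**Conclusion.** The false-positive limit in 12.C is wrong as written, by a small amount. The uncorrected test that yields n = 52 rejects from 31/52, with an exact false-positive rate of 10.6% against a stated maximum of 10%. The sample size is correct, and the 90% power claim holds at 90.6%.

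This is minor, and it does not call for a larger trial or a different test. Its practical use is to settle the result 31/52, on which the corrected and uncorrected tests disagree. The exact figures rest on a null rate of exactly 50%, an alternative of 67.3%, and known 1-year status for all 52 patients. The silence on unknown status is a separate gap in detail and not part of the arithmetic error.

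**What to change.** Keep n = 52 and the chi-square test. In 12.C, replace the two sentences that give maximum probabilities with text such as:

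> The regimen will be considered promising if at least 31 of 52 evaluable patients are progression-free at 1 year (one-sided chi-square test, 0.10 level, no continuity correction). The exact binomial false-positive rate of this rule is 0.106 at a true 1-year PFS of 50%. Its exact power at 67.3% is 0.906 (false-negative rate 0.094). These values assume that 1-year status is known for all 52 patients.

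Add one sentence saying how a patient with unknown 1-year status is counted. If the number evaluable is not 52, the same test and level give the cut-off.

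Only if the sponsor wants a false-positive rate strictly at or below 0.10 with 52 patients should it state at least 32 of 52 instead, with 0.063 and power of 85%.

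The cost is two sentences rewritten and one added. Under the 31/52 rule the sample size, test and power are unchanged, and the stated false-positive rate becomes slightly less favourable (0.106 instead of 0.10).
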